## Interventions and Duration

The Shed-MEDS Intervention (Figure 1. Stage 2) includes identification of medications for deprescribing, a surrogate preference interview, and discussion with residents' primary care providers (ALF and outside providers). The intervention ends after the final agreed upon deprescribing actions were communicated to the ALF providers. Follow-up data collection and assessments were conducted at 30-, 60-, and 90-days after completing intervention.

## Study Population and Sample Size

The eligible patient population are ALF residents with a dementia diagnosis, age  $\geq 65$  with polypharmacy as defined by  $\geq 5$  medications (or the presence of at least 1 PIM). The expected enrollment is 40 PWD with an estimated attrition rate of 10-15%.

# PARTICIPANT RECRUITMENT AND ENROLLMENT

## Eligibility Screening and Recruitment

The Vanderbilt University Institutional Review Board (IRB) requires a multi-stage recruitment process that allows residents and/or their surrogates the opportunity to opt out of contact with the research team. The research team is not permitted to screen ALF records for eligibility or reach out to residents and/or their surrogates directly. The ALFs are responsible for distributing project information to eligible residents' designated surrogates. Inclusion Criteria: (1) a documented Alzheimer's Disease or Related Dementia (ADRD) diagnosis; (2) resident is aged 65 years or older; (3) taking 5 or more medications OR at least 1 potentially inappropriate medication as defined by the Beers criteria, STOPP criteria, and RASP list.

## Enrollment Procedures

The first step of the recruiting process is for the Facility Administrator to notify surrogates that the study will take place. The administrator will send a letter (via email) to each resident's legally authorized representative and, if applicable, the resident. The letter will contain information about the study (e.g., eligibility criteria), the PI's contact information, and the date/time of the Town Hall meetings where the study will be discussed. The letter will let surrogates know that neither Town Hall attendance nor study participation are mandatory. It will also ask surrogates to notify the facility if they wish not to be contacted by the research team.

Additionally, the surrogate decision maker of each respective resident will receive a study information packet that includes a cover letter, two (2) copies of the consent documents, a study brochure, a release of information (ROI) authorization form, and a self-addressed and stamped envelope. The study team will create these packets, and facility staff will mail them to all surrogate decision makers of residents. Surrogates may sign a consent form and return to the research team in the envelope provided, or they may contact the PI for further discussion about participation. If the surrogate indicates interest in participating in the study but would like to discuss it with PI or KSP via a face-to-face meeting, the study team will arrange a time to meet at the facility to further discuss participation and sign the consent form.

The facilities regularly host Town Hall-style meetings for family members to facilitate communication between the staff and family members. The Principal Investigator and key study personnel (KSP) will attend Town Halls to explain the study in lay terminology emphasizing that participation is voluntary and choosing not to participate will not impact the resident's care. During the Town Hall meeting, residents and their surrogates will be given an opportunity to ask any questions they may have about the study and to provide comments; also, the study brochure will be made available. We will emphasize that all deprescribing decisions require both resident/surrogate agreement and the agreement of the facility clinicians. At the Town Halls, study team members will ask residents' surrogate decision makers if they would like to enroll their resident or be contacted by phone with more information about the study.

Any member of the research team can obtain written informed consent from an eligible resident and/or their surrogate using the IRB stamped and current dated copies of the informed consent document. Consent can be obtained either via mail (see packets mailed above) or in-person at the facility. When reviewing the consent document with the resident and/or surrogate, the research staff will give them time to review the document before the staff summarizes each section and addresses frequently asked questions. Staff should provide a second copy of the consent form to leave with the resident and/or surrogate.

During the informed consent process, study personnel will continuously reiterate the following:

- Data is collected only for research purposes.
- There is no obligation to participate and refusal to participate will not affect the resident's routine care.
- Residents/surrogates can withdraw from the study at any time

## STUDY PROCEDURES

Data collection includes resident descriptive data as well as four groups of outcomes: medications, quality of life, safety, and feasibility. Table 1 shows a summary of the study timepoints along with the corresponding assessments. Upon enrollment, residents and their surrogate complete interviewer-administered questionnaires, which require approximately 30 minutes. Descriptive, medication, and safety data are obtained via records request from the ALF at enrollment and the three follow-up time points. Interviewer-administered questionnaires are conducted again 90-days after intervention ends. All interview assessments are completed by a trained research geriatric nurse practitioner.

### Schedule of Assessments

**Table 1. Data Collection Schedule**

Measures	3-month Retrospective Review ∞	Enrollment	30- & 60-day Follow-up	90-day Follow-up
Demographics and Health Status				
Age, Gender, Race/Ethnicity, Education Level*		X		
Comorbidities*		X		
Cognitive Impairment (BIMS)	X*	X		X
Status: Long-Term Care, Hospice, Death*	X	X		X
Medications				
Total number of medications*	X	X	X	X
Sedative & Anticholinergic Drug Burden Index	X	X	X	X
Quality of Life				
DEMQoL-Proxy		X		X
BPSD*	X	X	X	X
Safety				
Falls*	X	X	X	X
Emergency Room Visits & Hospitalizations*	X	X	X	X
Feasibility				
RPATD (surrogate)		X		
Surrogate agreement w/ deprescribing recommendations		X	X	
Provider agreement w/ deprescribing recommendations		X	X	
Total number of conversations w/ prescribing MD/NPs		X	X	X
Total number of conversations with surrogates		X	X	X

### Descriptions of Assessments

**Demographic and Administrative Data:** The sociodemographic data collected during this investigation is obtained from the ALF medical record. Utilizing a standardized form to abstract information from the electronic medical record, a member of the project team collects age, gender, race/ethnicity, insurance status, outpatient providers, and highest education level. These data are verified with the surrogate during the baseline interviews.

Charlson Comorbidity Score ranges from 0 to 31, with a higher score indicating more comorbid illness. There is an additional one-unit increase in the weighted score for every decade starting from age 50. Data sources for comorbidities are the ICD-9 and ICD-10 diagnostic criteria found on the patient's Problem List in the EMR from the last 12 months.

Cognitive Impairment: The Brief Interview for Mental Status (BIMS) is a short, validated assessment of cognitive impairment with a total score range from 0 to 15 (0-7: severe impairment; 8-12: moderate impairment; 13-15: cognitively intact). The BIMS is routinely used in the SNF and long-term care settings.

### **Primary Outcomes - Medications**

Total number of Medications: The primary data source is the resident's ALF medication administration record (MAR). We include both prescription and over-the-counter medications (OTC) (vitamins, herbal supplements also included) administered by the following routes: oral, intravenous, intramuscular and ophthalmologic medications. All surrogates receive a baseline structured interview with specific prompts for OTC medications they may be providing directly (and not administered by the facility).

PIMs are defined by previously published lists including the recently updated Beers criteria, the STOPP criteria, as well as the RASP list, for which there is a large degree of overlap. The total number of PIMs is the sum of medications that are found on any of these explicit lists.

Drug Burden Index (DBI): A DBI score is calculated separately for anticholinergic (DBIAC) and sedative medications (DBIs), which have been strongly linked to functional impairment, falls, and delirium. The drug burden is the sum of each individual anticholinergic/sedative medication's prescribed daily dose divided by the sum of the minimum effective dose (as estimated by the FDA minimum recommended dose) and the patient's daily dose. The DBI includes over-the-counter medications. We will calculate the DBI at baseline and all follow-up timepoints. Importantly, the DBI captures reductions in dose, even when total number of medications is not reduced.

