## Study Design and Outcomes Overview

This is a single arm pilot and feasibility study to adapt the Shed-MEDS intervention to the memory care setting. The Shed-MEDS intervention is a multistep deprescribing protocol which considers patient and disease factors, life expectancy, goals of care, and appropriate treatment targets. Medication-specific factors such as drug-drug interactions, drug-disease interactions, and drug-specific safety profiles are also incorporated. Finally, patient preferences and primary prescriber input are key to final deprescribing actions by identifying the medications patients are willing to deprescribe and seeking their primary prescriber's agreement. In this intervention, deprescribing is defined as either stopping a medication or reducing the dose/frequency of a medication.

The primary study setting is two assisted living facilities (ALFs) with dedicated memory care units.

Eligible residents are ALF residents aged 65 years or older with a dementia diagnosis and experiencing polypharmacy as defined by 5 or more medications.

Primary Outcome is the number of medications deprescribed, either stopped or reduced dose, 90-days after intervention completion.

Secondary Outcome is the impact of deprescribing on behavioral symptoms of dementia and resident quality of life.

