### Outcomes

Aim 1: Descriptive statistics (counts and proportions for categorical variables and means and SDs for continuous ones) will be used to describe Demographics at baseline, as well as Feasibility outcomes in Aim 1 at each measurement.

Aims 2 and 3: All statistical tests will be two-sided, with alpha = 0.05. For Aims 2 and 3, we will be applying a within-subjects intervention design to estimate the effect size of Shed-MEDS deprescribing intervention on Medication and Quality of Life outcomes. This design takes advantage of the smaller sample size in this pilot intervention, with each subject's 3-month retrospective review serving as their own control, which also removes the between-subjects differences in each condition. For the Medications outcomes in Aim 2 and the Quality of Life outcome of BPSD in Aim 3a, changes during the intervention period will be modeled using GEE, where time (multiple indicators), intervention group (one indicator) and their interaction will form the predictors, controlling

for baseline demographics. Hypothesized differences between the intervention and control groups will be examined using appropriate linear contrasts. For the DEMQoL-Proxy in Aim 3a, we will use a two-sample t-test to compare measurements at baseline with the 90-day follow-up, which is robust against normality or heterogeneity of variance.

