## Data Analyses

Missing Data: We will examine the incidence of missing data for each outcome in Table 2. We acknowledge that although the missing data could be informative due to intervention-related death or surrogate decision, we will not have enough data to formally test it due to the extremely small number of anticipated attrition (<5).

Repeated measures: Barring study withdrawal or death, main outcomes including the total number of medications, Quality of Life, and Safety will be assessed at four time points (enrollment, 30, 60, and 90 days) for each participant. We account for the anticipated positive correlations using a generalized estimating equation (GEE) framework for each repeated outcome. Unlike the parametric generalized mixed-effects models, GEE imposes no mathematical model for data distribution, thus providing valid inference for a broader class of data distributions.

Limitations: There are a number of limitations that must be acknowledged in this pilot deprescribing study. The most apparent is the limited sample size. Although small, the sample size is sufficient to understand the primary feasibility aims of our study, applying Shed-MEDS in this novel population of PWD in an ALF. We have selected a within-subjects study design to maximize the power to estimate effect sizes on medication and quality of life outcomes for subsequent larger randomized trials. Without a concurrent, randomized comparator, there is a potential for time-related threats to validity, as we cannot control the effects of time on the outcomes. Furthermore, we would not be able to rule out carryover effects of earlier treatments on the outcomes.

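### Does asking about family-supplied OTC products only at baseline create a false fall in the medication count and DBI?

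*Combined protocol and SAP*

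**What the plan says.** Under Primary Outcomes - Medications, the count is drawn mainly from the MAR and covers prescription and OTC items, including vitamins and supplements. The same paragraph ends: "All surrogates receive a baseline structured interview with specific prompts for OTC medications they may be providing directly (and not administered by the facility". On the DBI, the section says: "The DBI includes over-the-counter medications. We will calculate the DBI at baseline and all follow-up timepoints". Neither sentence says what happens to a product that only the surrogate reports.

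Study Procedures gives the source by time point: "Descriptive, medication, and safety data are obtained via records request from the ALF at enrollment and the three follow-up time points". It adds: "Interviewer-administered questionnaires are conducted again 90-days after intervention ends". The OTC prompts are not named among those repeated questionnaires.

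Table 1 schedules "Total number of medications", marked with an asterisk, at the retrospective review, enrollment, 30 and 60 days, and 90 days. The footnote that explains the asterisk is not in the copy available for review.

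On analysis, the Outcomes part of Statistical Considerations describes each resident's "3-month retrospective review serving as their own control". The repeated-measures paragraph under Data Analyses says that "the total number of medications, Quality of Life, and Safety will be assessed at four time points (enrollment, 30, 60, and 90 days". Study Design and Outcomes Overview states: "Primary Outcome is the number of medications deprescribed, either stopped or reduced dose, 90-days after intervention completion".

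**The concern.** The interview sentence sits inside the definition of the count, the MAR is called the primary rather than the only source, and OTC items are said to be included. One natural reading is therefore that family-supplied products are added at enrollment. A product the facility does not administer would not be expected on its MAR, so it would be missing from a records-based count at 30, 60 and 90 days. It would look stopped when it was not.

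The error would run in the hypothesized direction, towards fewer medications and a lower DBI. With one arm it would not cancel. The repeated-measures analysis starts at enrollment, and Sample Size & Attrition says the pilot data will guide the power analysis of the multi-center trial, so an inflated effect could carry into that design.

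**Working it through.** The plan states no figure to reproduce; it says no formal power analysis is done. The check has two parts.

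**1. Which source does the text point to?**

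- Primary Outcomes - Medications: the MAR is the primary source, and no second source is said to contribute to the count.
- Study Procedures: facility records supply medication data at enrollment as well as at each follow-up. Enrollment is not treated differently.
- Pre-Review: the nurse practitioner identifies target medications from medical record data alone.
- Table 1: the other starred rows that can be checked against Descriptions of Assessments and the secondary-outcome definitions are record-derived (demographics, comorbidities, BPSD, falls, emergency visits and hospitalizations). The interview measures, DEMQoL-Proxy and rPATD, carry no star. BIMS is starred only in the retrospective column, where no interview is possible. The star probably marks data taken from the record, and the count row has it. This is inference, since the footnote is missing. The DBI row has no star, so the pattern says nothing about the DBI directly.
- Including OTC items in the count and DBI is satisfied by OTC items on the MAR. It does not require adding interview-reported products.

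One source at every point is the reading that fits all of these.

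**2. How large would the artefact be under the other reading?**

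It needs three things together: the products enter the enrollment value, they are not carried forward, and nobody asks again.

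Inputs from the documents: 40 enrolled with 10-15% attrition (Study Population and Sample Size), so 40 × 0.90 = 36 to 40 × 0.85 = 34 completers; a mean of 7.78 medications at the first facility (Study Setting); two-sided alpha 0.05 (Outcomes).

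Assumptions, because the documents give neither: a share p of residents with one such product, and an SD of true change between 1.0 and 3.0.

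Formulas: mean false fall = p; SD of observed change = √(SD² + p(1 − p)); noncentrality = p√n / SD of observed change. The rejection rate is that of a two-sided 5% paired t-test with no true change. This is a stand-in for the planned GEE.

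Worked case: p = 0.3, SD = 1.0, n = 36. SD of observed change = √(1 + 0.21) = 1.10; noncentrality = 0.3 × 6 / 1.10 = 1.64; rejection rate 0.356.

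| p (assumed) | False fall | Share of 7.78 | Rejection rate, SD 1.0-3.0, n 34-36 | At SD 3.0 alone |
|---|---|---|---|---|
| 0.1 | 0.1 | 1.3% | 0.054-0.087 | 0.054 |
| 0.3 | 0.3 | 3.9% | 0.087-0.356 | 0.087-0.089 |
| 0.5 | 0.5 | 6.4% | 0.154-0.742 | 0.154-0.160 |

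DBI: by the plan's formula, an anticholinergic or sedative product taken at its minimum effective dose scores 1/(1 + 1) = 0.5. If 5% or 10% of residents had one (assumed), the mean would fall by 0.5 × 0.05 = 0.025 or 0.5 × 0.10 = 0.05. This also needs a dose, which the plan does not say the interview collects.

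**What is spared.** With MAR-only data at both ends, the retrospective-to-90-day contrast has zero shift and the nominal 5% rate. The number deprescribed is not inflated if it is taken from the list agreed by surrogate and provider (Final Deprescribing Actions), because the targets come from records.

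**The case for a change.** The strongest case for a change is that the gap is real. Nothing excludes these products, carries them forward or repeats the prompts. Follow-up contacts exist (utilization questions at each time point, weekly follow-up, the 90-day questionnaires), but none is said to ask about OTC use. The direction of any bias is known and favours the hypothesis, and one sentence would settle the matter.

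It stands that the sentence is missing, and that the mixed reading would bias contrasts from enrollment. It would also put a false rise between the retrospective review and enrollment. It does not follow that the plan produces this bias. The stated source is the same at every time point, and the missing footnote and interview forms may already hold the rule.

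Nor would a written MAR-only rule remove every doubt. If the facility stops an item and the family goes on supplying it, MAR-only data show a reduction. Each such move shifts the mean change by 1/36 = 0.028 to 1/34 = 0.029, and it cannot be seen unless the prompts are repeated. Every way of handling these products has some cost.

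**Conclusion.** No change to the plan is needed. The handling of family-supplied OTC products is unwritten, but the plan's own statements on source lead an analyst to facility records at every time point, where the artefact is zero. The baseline interview can then stand as description.

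The conclusion rests on reading Study Procedures as governing the count and DBI at enrollment too. The likely meaning of the Table 1 star supports this for the count but does not prove it. If the reading were wrong, enrollment-based contrasts would be biased by the mean number of such products per resident. That number is unknown: at an assumed 10% of residents the effect is slight (0.1 medications, rejection rate about 5-9%), and the highest rate, about 74%, needs half of residents affected together with an SD of change of 1.0. Aims 2a and 2b compare with a pre-intervention period, and that contrast is untouched if both ends come from records. In a pilot with no formal power analysis, this is missing detail and not a flaw in the design.

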### **Secondary Outcomes – Quality of Life, Safety, and Feasibility**

Dementia Quality of Life Instrument – Proxy Version (DEMQOL- Proxy): The DEMQOL-Proxy scale is used to evaluate health-related quality of life in participants with severe dementia as rated by their caregivers. It is a 31-item version (DEMQOL-proxy, rated by the caregiver). Both versions are recommended for evaluating participants (and their caregivers) with mild to moderate dementia. The DEMQOL total score ranges from 28 to 112. The DEMQOL-proxy has 31-items which are reported on a four-point Liker scale (a lot/quite a bit/a little/not at all) with a total score range from 31 to 124. Higher scores indicate a better health-related quality of life.

Behavioral & Psychological Symptoms of Dementia (BPSD): The total number of BPSD episodes recorded. The following portions of the medical chart should be requested for review: nurses notes and incident reports. To tally the total number, the reviewer (KSP) should highlight each individual episode that requires intervention or redirection from staff, or accounts for declining care (such as refusing a shower). Documented episodes may mention physical or verbal aggression or agitation, episodes of wandering into others' rooms, or off the unit, episodes of packing up belongings or taking items belonging to others.

Falls: Falls are highly prevalent in this population and lead to fatal and non-fatal injuries. To determine the total number of falls, the following portions of the medical chart should be requested for review: Nursing notes, incident reports, monthly falls report. KSP should compare each event's source with other sources to avoid double-counting falls.

Unplanned Healthcare Utilizations: Request incident reports and nursing notes of all residents who visited the emergency department or had a hospitalization. All documented emergency department visits and hospitalizations need to be tallied and recorded on the chart abstraction data sheet.

Revised Patients' Attitudes Toward Deprescribing (rPATD) is a 19-item survey with 5-point Likert scale ranging from 'strongly agree' to 'strongly disagree.' Examples include: "I feel that I am taking a large number of medicines" and "I believe that all my medications are necessary." There is not an overall, global score for the assessment. Instead, a score ranging from 1-5 is assigned for each of the five factors: Burden, Appropriateness, Concerns about stopping, and Involvement. Higher scores in the burden, concerns about stopping, and involvement in treatment domains indicate a greater burden, concern, involvement. Questions regarding the appropriateness factor are scored in reverse. Thus, higher scores in the appropriateness domain indicate a participant's/surrogate's belief in the appropriateness of their medications. This tool was validated for use with surrogates.

Surrogate agreement with study deprescribing recommendations: The total number of medications the surrogate agrees to deprescribe will be totaled. For analysis purposes, medications will also be organized into medication classes.

Provider agreement with study deprescribing recommendations: The total number of medications the medical provider (i.e. Abe's Garden MD/NP or outside provider) agrees to deprescribe will be totaled. For analysis purposes, medications will also be organized into medication classes.

Total number of conversations with surrogates: We will record the total number of conversations with surrogates about the resident and the deprescribing process.

[figure not shown]
Total number of conversations with prescriber: The total number of conversations with the prescribing MD/NP as they are related to the deprescribing process will be recorded.

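### BPSD is compared as a raw episode total with no exposure term; most counting windows are unstated, and with a single look-back total the group and group-by-time terms are not estimable

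*Combined protocol and SAP*

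**What the plan says.** The Secondary Outcomes section defines the measure as "The total number of BPSD episodes recorded", tallied by a reviewer from nursing notes and incident reports. It gives no counting period and no denominator.

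Table 1 marks BPSD under "3-month Retrospective Review" and again at enrollment, at 30 and 60 days, and at 90 days. Study Procedures describes medication and safety data as "obtained via records request from the ALF at enrollment and the three follow-up time points", and Interventions and Duration says "Follow-up data collection and assessments were conducted at 30-, 60-, and 90-days after completing intervention". Both give the timing of collection, not the days that a count covers.

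Under Statistical Considerations, Outcomes, the control condition is each resident's "3-month retrospective review serving as their own control". BPSD shares a GEE with the medication outcomes, in which "time (multiple indicators), intervention group (one indicator) and their interaction will form the predictors", adjusted for baseline demographics. Data Analyses then says that the main outcomes, quality of life among them, "will be assessed at four time points (enrollment, 30, 60, and 90 days) for each participant", with the proviso "Barring study withdrawal or death". The look-back is not in that list. Neither section names a rate, an offset, days observed, or a link and family for the counts.

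**The concern.** A medication count or a Drug Burden Index describes a state on a given day. BPSD accumulates, so a total means something only relative to the days over which it was counted. The plan uses one model form for both kinds of outcome and carries no exposure information for the second.

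The model description also sits badly with a single-arm study. The group indicator can only mean control period versus intervention period. Unless the control period supplies several time points, period and time cannot be separated.

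Aim 3a is a no-harm hypothesis on BPSD at 90 days, tested two-sided at 0.05, and the estimates are meant to guide a larger trial. An analyst who has to settle the windows afterwards could, without intending it, conceal a worsening or manufacture one.

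**Working it through.** The plan gives no event rate, power or effect figure for BPSD, so there is no stated figure to reproduce. The check covers estimability, then the effect of window length.

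**Inputs.** Occasions: Table 1 and Data Analyses. Model terms and control: Outcomes. Enrollment of 40 and attrition of 10–15%: Study Population and Sample Size. Average stay of 1.6 years: Study Setting, first facility only. Everything else is labelled as assumed.

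**1. Estimability.** With k occasions, each belonging to one period only, intercept + time + group + interaction has 1 + (k−1) + 1 + (k−1) = 2k columns. There are only k distinct rows, so the rank is at most k. Baseline demographics do not vary over time and do not help.

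| Records per resident | Columns | Rank | Group estimable | Interaction estimable |
|---|---|---|---|---|
| One look-back total, 30, 60, 90 | 8 | 4 | no | no |
| One look-back total, enrollment (coded pre or post), 30, 60, 90 | 10 | 5 | no | no |
| Enrollment, 30, 60, 90 | 8 | 4 | no | no |
| Look-back forced to share enrollment's time level, enrollment coded post | 8 | 5 | at that level only | no |
| Three 30-day windows before, three after | 6 | 6 | yes | yes |

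In the first three rows the rank equals the number of occasions, so every occasion mean is estimable. Where the look-back is included, so is the 90-day minus look-back contrast.

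**2. Window length.** At a constant rate the expected raw ratio is days counted after ÷ days counted before. All windows except the three-month look-back are assumed.

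- Matched: 90/90 = 30/30 = 1.0.
- 30-day interval against one three-month total: 30/90 = 0.33. A true tripling would read 3 × 30/90 = 1.0.
- Cumulative follow-up against one three-month total: 30/90, 60/90, 90/90 = 0.33, 0.67, 1.00.
- Cumulative follow-up against 30-day look-back slices: 30/30, 60/30, 90/30 = 1.0, 2.0, 3.0.
- Four time points only, with enrollment as comparator: 90/30 = 3.0 if it covers 30 days and follow-up is cumulative; 30/90 = 0.33 if it covers 90 days and follow-up is per interval.
- If 14–30 days (assumed) from enrollment to intervention completion fall into the first follow-up count: (90+14)/90 = 1.16 to (90+30)/90 = 1.33 for the cumulative 90-day count.

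**3. Partial windows when both spans are nominally 90 days.** Attrition a of 0.10 or 0.15, spread evenly, loses a/2 = 5% or 7.5% of follow-up days. Treat 1.6 years as mean time since admission and three months as 0.25 years. Residents admitted recently then shorten the look-back by 0.25/(2 × 3.2) = 3.9% if tenure is uniform on 0–3.2 years, or by 1 − (1.6/0.25)(1 − e^(−0.25/1.6)) = 7.4% if it is exponential.

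- Leavers' truncated counts enter, (1 − a/2)/(1 − loss): 0.925/0.961 = 0.96 to 0.950/0.926 = 1.03.
- Leavers have no 90-day record, 1/(1 − loss): 1/0.961 = 1.04 to 1/0.926 = 1.08.

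**4. Simulation.** Assumed: 40 residents, 250 runs per scenario, Poisson log-link GEE, gamma frailty, 1 or 4 episodes a month, 12.5% attrition, exponential tenure; the contrast is at 90 days or month 3.

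| True ratio | Comparison | Median estimate | Significant |
|---|---|---|---|
| 1.0 | Total v 30-day interval | 0.34–0.35 | 100% improved |
| 1.0 | 30-day slices v cumulative | 3.04–3.05 | 100% worse |
| 1.0 | 90 v 90 days, no offset | 1.07 | 7–12% worse |
| 1.0 | Matched months with offset | 1.00–1.01 | – |
| 1.5 | Total v 30-day interval | 0.52 | 94–100% improved, 0% worse |
| 1.5 | Matched months with offset | 1.50–1.51 | 50–98% worse |

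A separate null simulation (36 residents, 300 runs, 0.5–6 episodes per 30 days, pre/post indicator only) agreed. Interval counts without an offset gave about 0.33 and 100% rejection. Keeping the look-back as one total and adding a log(days) offset gave 0.996–1.013, with 5–9% rejection.

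**The case against.** **The single total is an inference.** It comes from one column of Table 1. That column carries a footnote marker and the BPSD row an asterisk, and neither footnote is legible, nor is Figure 1. A window rule or a monthly split could be written there. Crossing several time indicators with a period indicator itself hints at several control-period time points. This stands, and it is why the aliasing is stated conditionally.

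**The four-time-point list may be loose.** It puts quality of life at all four, whereas Table 1 has DEMQOL-Proxy only at enrollment and 90 days. A reader might infer that the look-back is left out of the analysis. The documents do not establish that; they show two sections that disagree.

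**A reader might infer that the model cannot be fitted or that Aim 3a cannot be tested.** That goes too far. Dropping aliased columns leaves fitted values unchanged and introduces no bias, and Outcomes says hypotheses will be tested through linear contrasts, so a 90-day versus look-back contrast remains available. Bias comes from unequal windows, not from the aliasing.

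**A reader might take 0.33 or 3.0 as the expected error.** No passage sets the windows that produce them, and the simulated rejection rates follow directly from those assumed mismatches. A three-month look-back and follow-up to 90 days are nominally equal spans.

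**The stakes are limited.** BPSD is a secondary outcome in a pilot with no formal power analysis. The plan admits time-related threats to validity, and hospitalizations, emergency visits and deaths are reviewed separately. This lowers the urgency but does not supply the missing rule.

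**Conclusion.** The point holds in conditional form and should be fixed. Three things are firm on the legible text: BPSD is a raw total, no exposure term is named for its GEE, and Data Analyses omits the period that Outcomes uses as control. The lengths of the enrollment, 30-, 60- and 90-day counts, and whether they are per interval or cumulative, are not stated there, though the unreadable footnotes and figure may say.

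If the look-back is one total, or if only the four listed time points are used, the group term is aliased with time and the interaction is not estimable. It is the parameterisation that fails, not every comparison.

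The size of any bias depends on the windows. It is about −4% to +8% if both spans are 90 days, given the attrition and tenure assumptions, which borrow one facility's average stay. The ratios of 0.33 and 3.0 are illustrative extremes in opposite directions. Confidence is medium because of the unreadable footnotes and figure.

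**What to change.** - Abstract BPSD by event date. State in Table 1 the days that each entry covers and that counts are per interval.
- Count in three 30-day look-back windows matched to three non-overlapping 30-day windows after intervention completion, which makes the planned interaction estimable. Alternatively, replace group-by-time with a pre/post contrast.
- Record resident-days observed in each window, so that deaths, withdrawals and recent admissions are handled.
- Analyse BPSD as a rate, with a log-link count GEE and log(days) as offset, and name the family.
- State what the enrollment entry contributes and where days between enrollment and intervention completion are counted.
- Reconcile the time points in Data Analyses with the control period in Outcomes. The medication outcomes share this model, so the same correction serves them. Treat falls and emergency or hospital counts as rates too if they are modelled.

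The cost is wording in Table 1 and the statistical section, plus slightly more chart abstraction (event dates and days observed) from records already requested. No extra visits are needed.
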